Part 2, the randomized withdrawal period (RWP), will allow blinded comparison to placebo while participants maintain a stable diet. Phe half-life ( $t_{1/2}$ ) in PKU is 24 hours, and a steady state is reached within 5 days. The 4-week duration in RWP will minimize time off active treatment while allowing blinded comparison to placebo.

Response to SYNBI934v1 varies based on individual factors related to GI physiology (e.g., gastric pH, GI transit time) as well as total intake of dietary Phe. Subjects achieving  $\geq 20\%$  blood Phe lowering in DEP will be considered responders and will be included in the primary efficacy analysis population. A 20% change in biomarker level exceeds assay variability and can generally be considered biologically meaningful and was therefore selected as the threshold for responder definition.

The OLE will enable collection of long-term safety and efficacy data for up to 36 months. Dietary intake of Phe may be modified during the OLE based on measured blood Phe lowering if the recommended level of Phe  $< 240 \mu\text{mol/L}$  has been achieved. Dietary liberalization of natural protein while maintaining controlled Phe levels is of benefit to the participants and facilitates dietary compliance.

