### 8.4.2. Part 2: RWP

The RWP primary efficacy endpoint is the change from RWP baseline to Week 4 in blood Phe level. An MMRM analysis will be used to compare the mean change in blood Phe level between the placebo and SYNB1934v1 dose groups. The MMRM model will have treatment group, RWP

baseline blood Phe level, iTD dose level, visit, and visit  $\times$  treatment group (interaction effect), visit  $\times$  iTD dose level (interaction effect), and visit  $\times$  RWP baseline blood Phe level (interaction effect) as fixed effects. The MMRM will also incorporate the participant's repeated measures at visits Weeks 1, 3, and 4, with visit being treated as a categorical variable. Least-squares means for each treatment group and the SYN1934v1 treatment group difference from placebo, along with the corresponding [REDACTED] will be calculated for Weeks 1, 3, and 4. The primary efficacy analysis will compare the least-squares means treatment difference between SYN1934v1 and placebo in the change from baseline in the blood Phe level at Week 4.

At each of the scheduled assessments, blood Phe will be drawn in duplicate. The MMRM will incorporate these participant repeated measures. For the MMRM analysis, the results of each of the post-baseline duplicate samples from a visit will be included in the statistical model (i.e., without averaging the results within a given visit before inclusion into the MMRM).

The responder RWP FAS will be the primary efficacy analysis population.

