3.14.2.1 Primary Efficacy Endpoint Analysis

The RWP primary efficacy endpoint is the change from RWP baseline to Week 4 in blood Phe level. An MMRM analysis will be used to compare the mean change in blood Phe level between the placebo and SYNB1934v1 dose groups. The MMRM model will have treatment group, Screening Blood Phe (as a dichotomous variable: $\leq / > 720 \mu\text{mol/L}$), RWP baseline blood Phe level, iTD dose level, visit, and visit \times treatment group (interaction effect), visit \times iTD dose level (interaction effect), and visit \times RWP baseline blood Phe level (interaction effect) as fixed effects. The MMRM will also incorporate the participant's repeated measures at visits Weeks 1, 3, and 4, with visit being treated as a categorical variable. Least-squares means for both treatment groups and the SYNB1934v1 treatment group difference from placebo, along with the corresponding [REDACTED] confidence intervals and p-values will be calculated for Weeks 1, 3, and 4. The primary efficacy analysis will compare the least-squares means treatment difference between SYNB1934v1 and placebo in the change from baseline in the blood Phe level at Week 4.

At each of the scheduled assessments, blood Phe will be drawn in duplicate. The MMRM will incorporate these participant repeated measures. For the MMRM analysis, the results of each of the post-baseline duplicate samples from a visit will be included in the statistical model (i.e., without averaging the results within a given visit before inclusion into the MMRM).

The MMRM analysis will be based on the restricted maximum likelihood method. A Kenward-Roger approximation will be used for the denominator degrees of freedom. The covariance structure for the repeated-measures will be a direct product of unstructured (i.e., for the visits) and compound symmetry for the repeated assessments at a particular visit (i.e., the subject-level repeated measures has 2 dimensions, post-baseline Weeks 1, 3, and 4, as well as the 2 assessments at each visit. As such the covariance structure will use the direct product structure "UN@CS" as defined in SAS PROC Mixed).

For the dependent variable, this will be an observed-case analysis using the responder RWP FAS population, missing data will not be imputed.

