3.14.2.4 Key Secondary Efficacy Endpoint Analyses

The key secondary efficacy endpoint analyses for the RWP are provided below. These analyses will be performed on the responder RWP FAS.

- ***Percent change from DEP baseline in blood Phe level at Week 4***

The percent change from DEP baseline to Week 4 in blood Phe level, will be analyzed using an MMRM analysis similar to the model described for the RWP primary efficacy analysis ([Section 3.14.2.1](#)), with the dependent variable being the percent change in blood Phe level from DEP baseline, and the DEP baseline blood Phe level as the baseline blood Phe level covariate. This will be an observed-case analysis using the DEP FAS population, missing data will not be imputed. Note that if the MMRM model does not converge, the same methodology as described for the RWP primary efficacy analysis ([Section 3.14.2.1](#)) will be applied.

- ***Change from DEP baseline to Week 4 in blood Phe level***

The change from DEP baseline to Week 4 in blood Phe level, will be analyzed using an MMRM analysis similar to the model described for the RWP primary efficacy analysis ([Section 3.14.2.1](#)), with the dependent variable being the change in blood Phe level from DEP baseline, and the DEP baseline blood Phe level as the baseline blood Phe level covariate. This will be an observed-case analysis using the responder RWP FAS population, missing data will not be imputed. Note that if the MMRM model does not converge, the same methodology as described for the RWP primary efficacy analysis ([Section 3.14.2.1](#)) will be applied.

- ***Blood Phe level $\leq 360 \mu\text{mol/L}$ at Week 4***

The proportion of participants meeting the key secondary endpoint, Blood Phe level $\leq 360 \mu\text{mol/L}$ at Week 4, will be tested between the placebo and SYNB1934v1 treatment groups using a Fisher's Exact test. This will be an observed-case analysis approach using the responder RWP FAS such that if a participant is missing the data needed to determine the endpoint, they will be considered as not having met the endpoint.

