3.18.2.1 Missing at Random Multiple Imputation

Missing Blood Phe values will be imputed via multiple imputation (MI) assuming MAR for each of the following assessment visits (DEP Screening, DEP Baseline, RWP Baseline, RWP Week 1, RWP Week 3, and RWP Week 4). Note that at each scheduled assessment visit there are duplicate blood Phe measurements.

Fifty imputed datasets will be created.

The following are the set of variables to be used in the multiple imputation model:

- DEP Screening blood Phe
- DEP Baseline blood Phe (i.e., using the average of the duplicate values)
- iTD Dose level
- Randomized Treatment group (SYNB1934v1 or placebo)
- Previous RWP Baseline blood Phe values. For the duplicate blood Phe measures occurring at each scheduled visit, they will be “ordered” by the corresponding vial number:
 - RWP BaselineA and RWP BaselineB
 - Week 1A and Week1B
 - Week 3A and Week3B
 - Week 4A and Week4B

Here the “A” values correspond to the duplicate blood Phe value with the smallest vial number and the “B” values correspond to the duplicate blood Phe value with the largest vial number. If there is just a single corresponding vial for an assessment it will be assigned “A”.

The imputations will be performed using monotone linear regression imputation methods which will impute the participants’ blood Phe values at each of the scheduled assessment visits in the study (including the duplicate assessments at each scheduled visit).

If the missing data does not follow a monotonic pattern, a sequential approach to imputing the data via a Markov chain Monte Carlo (MCMC) method to produce a monotone missing data pattern will be applied using the MCMC impute=monotone option in Proc MI (SAS System). Following the method described in [Smith \(2017\)](#) the non-monotonic data imputation will be performed “by” the categorical treatment group variable. Then the monotone linear regression imputation methods will be applied.

Note: if the multiple imputation model does not converge or produce estimates (i.e., due to over-specification) the set of imputation variables may be modified.

Based on the complete Blood Phe datasets, the change and percent change from baseline in blood Phe levels will be calculated.

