3.20 Changes from the Protocol Planned Analyses

The following are the set of changes from the protocol planned analyses as specified in the study protocol.

These changes will be incorporated into the next study protocol amendment.

- In [Section 2.2.2.1](#), the handling of the scenario when a participant in the DEP de-escalates after RWP randomization is described.
- In [Section 2.5.1](#), the intercurrent events for the estimands were updated. In particular, participants whose dose is dropped during the interim analysis will not be excluded from the analyses.
- In [Section 3.5](#), the DEP FAS was updated to no longer exclude participants whose dose was dropped at the interim analysis.
- In [Section 3.5](#), the DEP FAS was updated to exclude those participants who did not take at least one dose of DEP study medication.
- In [Section 3.5](#), the RWP FAS, responder RWP FAS, and nonresponder RWP FAS were updated to exclude those participants whose dose was dropped at the DEP interim analysis.
- In [Section 3.5](#), the RWP FAS, responder RWP FAS, and nonresponder RWP FAS were updated to exclude those participants who did not take at least one dose of RWP study medication.
- In [Section 3.14.1.2](#), the DEP primary efficacy analysis, iTD was removed as a covariate from the MMRM.
- In [Section 3.14.2.1](#), the RWP primary efficacy analysis, Screening blood Phe was added as a covariate to the MMRM (i.e., as a dichotomous variable: $\leq / > 720 \mu\text{mol/L}$).
- In [Section 3.14.2.6](#), the testing order of the 3 key secondary endpoints in the RWP was not consistent within the study protocol between the synopsis and Section 8.9 of protocol. The correct testing order (i.e., consistent with Section 8.9 of the study protocol) is provided in this SAP.

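### The RWP primary model leaves out DEP baseline Phe and the DEP-baseline key secondaries leave out RWP baseline Phe: a modest, cheap gain in precision goes unused

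*SAP*

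**What the plan says.** - **RWP primary (SAP 3.14.2.1).** The fixed effects are treatment, "Screening Blood Phe (as a dichotomous variable" split at 720 µmol/L), then "RWP baseline blood Phe level, iTD dose level, visit, and visit" interactions with treatment, iTD and RWP baseline. Protocol 8.4.2 has the same model without the screening term. SAP 3.20 records the addition: "the RWP primary efficacy analysis, Screening blood Phe was added as a covariate to the MMRM". Continuous DEP baseline Phe is in neither version, and no reason is given.
- **Key secondaries (SAP 3.14.2.4).** For change and percent change from DEP baseline the model is similar to the primary, with "the DEP baseline blood Phe level as the baseline blood Phe level covariate". DEP baseline thus replaces RWP baseline.
- **Imputation (SAP 3.18.2.1).** The RWP imputation model contains both: "DEP Baseline blood Phe (i.e., using the average of the duplicate values") and the RWP baseline duplicates.
- **Population (Protocol 8.4.2).** "The responder RWP FAS will be the primary efficacy analysis population".
- **Time course (Protocol 1.6).** The Phe half-life "in PKU is 24 hours, and a steady state is reached within 5 days". Participants keep their DEP diet during the RWP (SAP 2.2).

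**The concern.** Each participant has two Phe levels before the first randomised dose: one off drug (DEP baseline) and one on drug (RWP baseline). With a short half-life and a fixed diet, a participant switched to placebo should drift back towards the off-drug level, while one kept on active should stay near the on-drug level. Week 4 Phe therefore depends on both values, and each model contains only one. The screening stratum is a coarse substitute: it treats 370 and 710 µmol/L as equal, and likewise 730 and 1,500.

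At stake is the width of the confidence interval for the confirmatory comparison, in a responder set likely to be small. Responder status is not known at randomisation (Protocol 1.6.1), so apart from that two-level stratum the set is balanced on off-drug Phe only by chance.

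**Working it through.** **1. Are both values safe to adjust for?** DEP baseline is taken before any drug. RWP baseline is taken before the first RWP dose. SAP 2.2.2.1 places the randomisation call a week before the RWP baseline visit, but participants are then still on open-label iTD and the assignment is blinded. Randomised treatment cannot have affected either value.

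**2. Why the omitted value predicts.** Let k be the fraction of return to the off-drug level on placebo. Then approximately:
- placebo: Week 4 − RWP baseline = k × (DEP baseline − RWP baseline) + noise
- active: Week 4 − RWP baseline = noise

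With only RWP baseline in the model, the k × DEP baseline part stays in the placebo residual. Simulation agrees: the partial correlation of DEP baseline with the outcome was 0.26-0.80 on placebo, 0.07-0.21 on active and 0.23-0.51 pooled.

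**3. The plan's own figures.** The protocol synopsis gives a difference of −245, SD 247, two-sided 0.05, 1:1 allocation, 5% dropout and an unadjusted t-test. N and power are redacted, so there is nothing to reproduce. A noncentral t calculation from these inputs gives:

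| Power | Per arm | Total | Total ÷ 0.95 |
|---|---|---|---|
| 80% | 17 | 34 | 36 |
| 85% | 20 | 40 | 43 |
| 90% | 23 | 46 | 49 |
| 95% | 28 | 56 | 59 |

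**4. Gain by partial correlation.** Residual SD = 247 × √(1 − ρ²), with ρ assumed and 23 per arm. This treats 247 as the SD left under the planned covariates.

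| ρ | Residual SD | Variance reduction ρ² | Power |
|---|---|---|---|
| 0 | 247 | 0% | 90.8% |
| 0.2 | 242 | 4% | 91.9% |
| 0.3 | 236 | 9% | 93.2% |
| 0.4 | 226 | 16% | 94.8% |
| 0.5 | 214 | 25% | 96.7% |

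**5. Simulation of the primary contrast.** Responders only, with a Week 4 ANCOVA standing in for the MMRM. The inputs below are assumptions.

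*Set A:* 23 per arm, planned covariates with and without DEP baseline. The plan's ratio is 245/247 = 0.99.

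| Mean off-drug Phe, between-person SD, visit CV, return | Difference / SD | Variance multiplier | Power without → with |
|---|---|---|---|
| 1200, 500, 10%, full | 563/242 = 2.33 | 0.74 | 1.00 → 1.00 |
| 1000, 400, 15%, full | 366/212 = 1.73 | 0.85 | 1.00 → 1.00 |
| 800, 300, 25%, full | 286/246 = 1.16 | 0.98 | 0.98 → 0.98 |
| 700, 250, 30%, full | 254/253 = 1.00 | 0.97 | 0.92 → 0.92 |
| 900, 350, 22%, 75% | 211/237 = 0.89 | 0.93 | 0.84 → 0.85 |

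Monte Carlo error on the multiplier is about 0.02-0.03.

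*Set B:* iTD and stratum in both models; mean 850, SD 350, mean reduction 28%; 34, 46 or 60 responders. The responder rule matters: SAP 2.2 assesses response at Week 3 of the iTD, whereas SAP 3.4.3 accepts it at any time in the DEP.
- iTD-only rule, CV 20%: model variance falls 9% (4-6% empirically).
- Any-time rule, CV 20%: falls 14-15%.
- Any-time rule, 75% return, 46 responders (221/220 = 1.00): falls 13% (12% empirically).
- CV 10-30%: falls 4-24% (iTD-only) or 9-26% (any-time).

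*Set C:* iTD in both models; mean 750 or 900, SD 300, mean reduction 30%, full return unless stated.
- CV 30%, near the plan's ratio: falls 4-6%; power moves between −0.4 and +1.4 points.
- CV 20% with half return: falls about 6%; power rises about 3 points.

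**6. Key secondaries.** The same argument runs in reverse: given DEP baseline, RWP baseline predicts Week 4 in the active arm. Estimates of the variance reduction vary widely. They were 0-14% with the stratum but not iTD in the model. For the absolute change with iTD included, they were 7-22% in one set of scenarios and 6-45% in another.

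**The case against.** The strongest reply is that nothing here is an error. The planned primary model adjusts for the endpoint's own baseline, iTD and the stratification factor, and power was set by an unadjusted t-test, so nothing promised is lost. A lean model is defensible in a small set that already carries iTD and its visit interaction. DEP baseline is one visit (two tubes from one venipuncture), so it measures the off-drug level with noise, and no withdrawal data are given to show full return. The largest gains arise at CV 10-15%, where power is already near 100%. In Set C, CV 10-20% gave a change SD of about 120-222, below the plan's 247.

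All of this stands as a limit on size. It does not reverse the expected direction or supply a reason for the omission, and the sponsor already treats DEP baseline as informative in the imputation model.

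A reader might infer more: that the omission biases the comparison, inflates type I error, leaves the RWP underpowered, or leaves the model with no off-drug information. The documents support none of these. The randomised comparison is valid without the extra term, and screening Phe is a coarse off-drug term. Nor should 25% be read as the expected gain; it is the top of an assumed range.

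**Conclusion.** This is a modest efficiency point. For the primary, adding DEP baseline lowers the variance of the Week 4 difference by about 0-25% under plausible assumptions, and by about 4-15% near the plan's 245/247 ratio. Set A's 2-7% at similar ratios puts the low end at a few per cent. A 4-15% fall is worth 1/0.96 − 1 = 4% to 1/0.85 − 1 = 18% more participants, or an interval narrower by 1 − √0.96 = 2% to 1 − √0.85 = 8%.

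The size depends on within-person variability, the degree of return on placebo and the responder rule, none of which the documents settle. The gain is an average: with 46 responders and CV 20%, model variance was smaller in 68% (iTD-only rule) to 82% (any-time rule) of replicates. In a small responder set with high visit-to-visit variability it may be close to nil. The key-secondary gain is less certain still, and the percent-change endpoint was not separately quantified with iTD in the model.

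**What to change.** Before the DEP and RWP are unblinded (SAP 2.2.3):
- add continuous DEP baseline Phe and visit × DEP baseline to the RWP primary MMRM;
- add RWP baseline Phe and visit × RWP baseline to the two DEP-baseline key secondary MMRMs;
- list both changes in SAP 3.20, as was done for screening Phe.

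The cost is SAP wording and 1 + (3 − 1) = 3 model degrees of freedom per analysis. No new data are needed.

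One consequence should be stated openly. The primary and the absolute-change key secondary differ only in which baseline is subtracted. Once both baselines are covariates in both models, that subtraction is absorbed, so on the same participants the two Week 4 treatment contrasts and p-values coincide. Type I error is unharmed, but that step of the fixed sequence then adds no separate evidence. The percent-change key secondary stays distinct.

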3.14.2.2 Primary Efficacy Analysis Model Does Not Converge

If the RWP primary efficacy MMRM analysis does not converge, the repeated measures at each blood Phe assessment will be averaged together and the average of the repeated measures will be used to calculate the change from baseline in blood Phe level, the dependent variable. The model will have change from baseline as the dependent variable. The model will have percent change from baseline as the dependent variable (i.e., using the averaged value at each of the Week 1, 3, and 4 visits). The MMRM model will be the same (i.e., same set of fixed effects as described in [Section 3.14.2.1](#)) with the exception that the covariance structure for the repeated-measures will be unstructured to account for the within-subject Week 1, 3, and 4 assessments. If this model does not converge, a compound symmetry covariance structure will be used.

3.14.2.3 Primary Efficacy Sensitivity and Supplementary Analysis

The following sensitivity and supplementary analyses will be performed for the RWP primary efficacy endpoint.

- **Imputation of Missing Data:** Multiple imputation methods will be used to impute missing blood Phe data during the RWP. The imputation of missing data analysis will be performed twice, once assuming the data is missing at random (MAR), and also assuming missing not at random (MNAR). The methodology for the multiple imputation is provided in [Section 3.18.2](#). The analysis model will be the same model as the RWP primary efficacy endpoint analysis.
- **Analysis of Covariance:** The primary efficacy endpoint will be analyzed using an analysis of covariance (ANCOVA) model. The change from RWP baseline to Week 4 in blood Phe level is the dependent variable, using the average of the duplicate Week 4 blood Phe levels (i.e., if one of the values is missing, the non-missing value will be used). The ANCOVA has treatment as a fixed effect and RWP baseline Phe is a covariate. This will be an observed-case analysis using the responder RWP FAS population, missing data will not be imputed.
- **Responder RWP PPS Analysis:** The primary efficacy endpoint analysis will be performed using the responder RWP PPS analysis set (defined in [Section 3.5](#)).
- **Responder Randomized set Analysis:** The primary efficacy endpoint analysis will be performed using the responder Randomized analysis set (defined in [Section 3.5](#)). Missing data will be imputed assuming the data is missing at random (MAR). The methodology for the multiple imputation is provided in [Section 3.18.2](#).
- **Responder RWP FAS Analysis Including Participants in a Dropped Dose:** The primary efficacy endpoint analysis will be performed using the responder RWP FAS analysis set (defined in [Section 3.5](#)) with the modification that participants whose dose was dropped at the DEP interim analysis are included in the analysis (i.e., this analysis will only be performed if one or more doses are dropped at the DEP interim analysis (see [Section 3.17](#)).

- ***Excluding Observations after Treatment Discontinuation, Antibiotic use, or Prohibited Medication:***

The primary efficacy endpoint analysis will be performed on the responder RWP FAS using an observed case analysis which excludes observations after the following intercurrent events occur in the RWP: Treatment discontinuation, antibiotic use, prohibited medication use.

Additionally, histograms illustrating the Week 4 change and percent change from baseline in blood Phe by treatment group will be produced.

3.14.2.4 Key Secondary Efficacy Endpoint Analyses

The key secondary efficacy endpoint analyses for the RWP are provided below. These analyses will be performed on the responder RWP FAS.

- ***Percent change from DEP baseline in blood Phe level at Week 4***

The percent change from DEP baseline to Week 4 in blood Phe level, will be analyzed using an MMRM analysis similar to the model described for the RWP primary efficacy analysis ([Section 3.14.2.1](#)), with the dependent variable being the percent change in blood Phe level from DEP baseline, and the DEP baseline blood Phe level as the baseline blood Phe level covariate. This will be an observed-case analysis using the DEP FAS population, missing data will not be imputed. Note that if the MMRM model does not converge, the same methodology as described for the RWP primary efficacy analysis ([Section 3.14.2.1](#)) will be applied.

- ***Change from DEP baseline to Week 4 in blood Phe level***

The change from DEP baseline to Week 4 in blood Phe level, will be analyzed using an MMRM analysis similar to the model described for the RWP primary efficacy analysis ([Section 3.14.2.1](#)), with the dependent variable being the change in blood Phe level from DEP baseline, and the DEP baseline blood Phe level as the baseline blood Phe level covariate. This will be an observed-case analysis using the responder RWP FAS population, missing data will not be imputed. Note that if the MMRM model does not converge, the same methodology as described for the RWP primary efficacy analysis ([Section 3.14.2.1](#)) will be applied.

- ***Blood Phe level $\leq 360 \mu\text{mol/L}$ at Week 4***

The proportion of participants meeting the key secondary endpoint, Blood Phe level $\leq 360 \mu\text{mol/L}$ at Week 4, will be tested between the placebo and SYNB1934v1 treatment groups using a Fisher's Exact test. This will be an observed-case analysis approach using the responder RWP FAS such that if a participant is missing the data needed to determine the endpoint, they will be considered as not having met the endpoint.

